#### *7.2. Study Records Retention*

The PI will retain investigational product disposition records, electronic database files, and source documents for the maximum period required by applicable regulations and guidelines, or as specified by the Sponsor, whichever is longer. Records with individual patient identifiers will be maintained for 10 years only. After this date, all records will be identified by subject number only with no connection to individual patients. The Sponsor will inform the PI when records are no longer needed.

#### *7.3. Clinical Monitoring Plan*

Representatives of Sponsor will be allowed to visit the study site periodically to assess the data, quality and study integrity. This will include: reviewing study records, compare records with source documents, discussing conduct of study with the PI and verifying the conditions of the facility. In addition, the study may be evaluated by Sponsor's auditors and government inspectors. They will be allowed access to source documents, electronic database, and other study files.

#### *7.4. Sample Size Consideration*

Sample size determination was based on the power to detect a significant effect of FMD nutritional intervention on fat mass during the treatment period (6 months) with respect to the control group. The primary hypothesis of this trial can be formally stated as a test of whether there is a time × intervention interaction. In particular, assuming a low effect size of the FMD intervention (Cohen's  $F = 0.10$ ) and a correlation coefficient among the repeated measures equals to 0.5, a sample size of 107 participants per group, would give a power of at least 0.9 for testing the hypothesis of whether there is a time × intervention interaction at a significance level of 0.05. With an estimated dropout rate of 30%, at least 153 participants would need to be recruited in each arm. For this reason, we will enrol 501 participants that will be randomly assigned to each of the three arms (167 for each arm).

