Efficacy assessments	
Primary objectives: linear mixed models will be used to compare arm 1 (FMD) and arm 2 (FMD+LD) to the arm 3 (control group) sitting fat mass expressed in terms of change from baseline to the visit 3.
 
Secondary objectives: linear mixed models will be used to compare FMD+LD and FMD to the control group sitting the following parameters expressed in terms of change from baseline to the visit 3: inflammatory biomarkers, IGF-1, blood pressure, serum lipids, glucose, CV biomarkers, body weight, BMI, body composition, insulin resistance, and aging biomarkers, proportion of participants who receive antihypertensive/hypoglycemic medications, sleep quality and duration.

Key safety assessments	AEs and AEs leading to discontinuation
Key words	Longevity Diet, Fasting Mimicking Diet, Body Composition

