### 2.2. Endpoints

[figure not shown]
2.2.1. *Primary endpoint*: change from baseline to end of study in body composition measured as percentage of fat mass.

2.2.2. *Secondary endpoints*: change from baseline to end of study in blood pressure, serum lipids, glucose, HbA1C, CV biomarkers (body weight, BMI, blood pressure, serum lipid levels and dysglycemia blood measurements), body weight, BMI, insulin resistance, telomere length, proportion of participants who receive antihypertensive/hypoglycemic medications, and sleep quality and duration using the Pittsburgh Sleep Quality Index, and the Berlin questionnaire.

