##### *7.7.1. Analysis supporting primary objectives*

Generalized mixed linear models will be used to compare arm 1 (FMD) to the arm 3 (control group) sitting fat mass expressed in terms of change from baseline to the end of the 3 FMD cycles (month 6, visit 3). The analysis will include the fixed categorical effect of treatment, a fixed term modelling changes between baseline and other time periods, as well as a random term accounting for repeated measurements on the same patients. The same analyses will be used to compare arm 2 to the arm 3, sitting fat mass expressed in terms of change from baseline to the end of the study (month 6).

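### Section 7.4's power of at least 0.9 at 107 per group fits only two-degree-of-freedom tests, not the pairwise month-6 comparisons that 2.2.1 and 7.7.1 make primary; the terms listed in 7.7.1 omit the treatment × time interaction

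*Protocol*

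**What the plan says.** **Sample size (7.4).** "Sample size determination was based on the power to detect a significant effect of FMD nutritional intervention on fat mass during the treatment period", compared with control. The primary hypothesis is then given as an interaction of intervention with time. The assumptions are Cohen's f = 0.10, correlation 0.5 among repeated measures and significance level 0.05. The result is that "a sample size of 107 participants per group, would give a power of at least 0.9 for testing the hypothesis". Dropout of 30% raises this to 153 per arm, and 167 per arm are to be enrolled. Section 7.4 does not give the number of groups or visits in the calculation, or the month-6 difference that f = 0.10 stands for.

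**Primary endpoint (2.2.1).** "change from baseline to end of study in body composition measured as percentage of fat mass".

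**Primary analysis.** The Protocol Summary compares both diet arms with control, "sitting fat mass expressed in terms of change from baseline to the visit 3". Section 7.7.1 does this as two comparisons, arm 1 vs arm 3 and then arm 2 vs arm 3, each on change to month 6. On the model it says: "The analysis will include the fixed categorical effect of treatment, a fixed term modelling changes between baseline and other time periods". A random effect for each participant's repeated values is added. No treatment × time term is listed.

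**Measurements (3.3.3 to 3.3.5, Table 1).** Bioelectrical impedance is done at baseline, month 3 and month 6.

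**The concern.** The stated power should belong to the test that decides the trial. A reader of 7.4 will take 0.9 as the power for FMD vs control at month 6. A time × intervention test is the same as that comparison only with two arms and two visits. With three visits it detects any difference in time course. With three arms it detects any difference among the arms. Neither has the power of the single contrast in 7.7.1.

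The model raises a second question. If treatment, time and a random subject term are fitted to repeated values without their interaction, the treatment term is an average over visits, so the quantity estimated is not the primary endpoint.

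**Working it through.** **1. Reproduce 107.** For the within-between interaction in repeated-measures ANOVA with k groups, m visits and N = k × n:

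λ = f²·N·m/(1−ρ), df1 = (k−1)(m−1), df2 = (N−k)(m−1), noncentral F, alpha 0.05.

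Inputs from 7.4: f = 0.10, ρ = 0.5. As k and m are not stated, several layouts were tried.

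| Groups × visits | df1 | Power at 107 | Smallest n for 0.9 |
|---|---|---|---|
| 2 × 2 | 1 | 0.830 | 133 |
| 2 × 3 | 2 | 0.902 | **107** |
| 3 × 2 | 2 | 0.902 | **107** |
| 2 × 4 | 3 | 0.948 | 90 |
| 3 × 3 | 4 | 0.956 | 87 |
| 3 × 4 | 6 | 0.982 | 74 |

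For 2 × 3, λ = 0.01 × 214 × 3/0.5 = 12.84; for 3 × 2, λ = 0.01 × 321 × 2/0.5 = 12.84. In both, n = 106 gives 0.899. Dropout also reproduces: 107/0.7 = 152.9, so 153. Enrolling 167 leaves 167 × 0.7 = 116.9, about 117 completers per arm.

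The arithmetic of 7.4 is therefore right, for a test on two degrees of freedom. The 2 × 2 layout, which is FMD vs control on change to month 6, would have needed 133 per group.

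**2. What f = 0.10 means at month 6.** For two arms with differences d_t at each visit, f² is the mean over visits of ((d_t − d̄)/2)²/σ². Let δ be the month-6 difference in SD units.

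- 2 × 2, differences (0, δ): f = δ/4, so δ = 0.40.
- 2 × 3, linear (0, δ/2, δ): f = δ/√24, so δ = 0.490.
- 2 × 3, complete by month 3 (0, δ, δ) or only at month 6 (0, 0, δ): f = δ/√18, so δ = 0.424.
- 3 × 2, both diets equal: f = δ/√18, so δ = 0.424 for each.
- 3 × 2, FMD with half the FMD+LD effect: FMD+LD 0.490, FMD 0.245.

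**3. Power of FMD vs control at month 6.** The variance of the change is 2(1−ρ)σ² = 1.00σ². The test is a two-sided two-sample t at 0.05 with noncentrality δ/√(2/n). For example, 0.40/√(2/107) = 2.93, which gives 0.83.

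| Reading of f = 0.10 | δ (SD) | 107 completers | 117 completers |
|---|---|---|---|
| Directly on baseline vs month 6 | 0.40 | 0.83 | 0.86 |
| 2 × 3, complete by month 3 or only at month 6 | 0.424 | 0.87 | 0.90 |
| 2 × 3, linear | 0.490 | 0.95 | 0.96 |
| 3 × 2, diets equal | 0.424 | 0.87 | 0.90 |
| 3 × 2, FMD half of FMD+LD | 0.245 | 0.43 | 0.46 |

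**4. The terms in 7.7.1.** If these are fitted to fat-mass levels at three visits, the treatment term estimates (0 + d3 + d6)/3. For a linear effect that is (0 + 0.5 + 1)/3 = 0.5 of the month-6 difference; for one complete by month 3 it is 2/3. If they are fitted to changes at months 3 and 6, it estimates (d3 + d6)/2, which is 0.75 of the month-6 difference for a linear effect. With the month-6 change score as the only response, it is the month-6 difference itself.

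**5. Baseline as covariate.** The variance becomes (1−ρ²)σ² = 0.75σ². For 0.40 SD, power rises from 0.83 to 0.92 at 107 and from 0.86 to 0.94 at 117. The variance ratio is (1+ρ)/2: 0.75 at ρ = 0.5 and 0.90 at ρ = 0.8, so the gain shrinks as ρ rises.

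**The case against.** **The layout is not stated.** The 3 × 2 layout uses the trial's own three arms and the two time points of the primary endpoint. On that reading 7.4 did power the month-6 change. This stands, and the point must allow for it. What remains is that the test is then an omnibus over three arms, while 7.7.1 makes two pairwise comparisons. The 2 × 3 layout fits 7.4's mention of FMD against control and the three impedance visits, but that too is inference.

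**The response may be a change score.** Section 7.7.1 speaks of change to month 6. If that single change is the response, the treatment term already carries the interaction. This also stands. However, the same section lists a term for changes between baseline and other time periods and a random term for repeated measurements, which suggests that more than one visit enters the model.

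**Model detail belongs in the statistical analysis plan.** Often so, and a baseline covariate is a gain in efficiency rather than the repair of a contradiction. But this protocol states both the hypothesis and the model terms, under its own heading for statistical analysis, and the two do not match.

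**Stronger readings to avoid.** A reader might infer that the trial is underpowered. The documents do not support that: most readings give 0.86 to 0.96 at the expected 117 completers, and the low figure needs both the 3 × 2 layout and a weaker FMD effect. A reader might also compute lower power for an effect that fades after month 3. Nothing in the protocol suggests fading; visits 2 and 3 are each described as month 3 or 6, or 5 to 7 days after an FMD cycle. Power figures for a treatment main effect on raw levels or averaged change would likewise be hypothetical, since no section names those as the primary test.

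**Conclusion.** The point holds as a mismatch between the test that was powered and the test that is primary. Both layouts that give exactly 107 are two-degree-of-freedom tests, and neither is the one-degree-of-freedom contrast of 7.7.1. The power of that contrast for FMD vs control at 107 completers runs from 0.83 to 0.95 on two-arm readings, and falls to 0.43 on the 3 × 2 reading if FMD has half the FMD+LD effect. Section 7.4 does not let a reader tell which applies.

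The omission in 7.7.1 is conditional: it matters if the listed terms are fitted to repeated values, and not if a single month-6 change score is the response.

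These figures assume ρ = 0.5 between all visits, equal variances, two-sided alpha 0.05 for each comparison, and for 2 × 3 an effect that does not fade. The plan should be corrected, but no increase in enrolment follows from this.

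**What to change.** **In 7.4**, name the groups and visits behind 107, and state the power for FMD vs control on change in percent fat mass to month 6, with the difference in SD units. The text depends on what was meant:

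- f = 0.10 directly on baseline vs month 6: 0.40 SD, power 0.83 with 107 completers per arm and 0.86 with 117.
- 2 arms × 3 visits: 0.42 SD (complete by month 3 or only at month 6) to 0.49 SD (linear), power 0.87 to 0.95 with 107 and 0.90 to 0.96 with 117.
- 3 arms × 2 visits: state the assumed effect of each diet; with equal effects 0.42 SD, power 0.87 and 0.90.

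**In 7.7.1**, add the treatment × time term, name its month-6 contrast as the primary test for each diet arm vs control, and adjust for baseline percent fat mass.

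**Cost.** Wording in two sections. No extra participants, visits or measurements are needed, since baseline fat mass is already measured.

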#### *7.6. Safety Review*

A review of the collected safety data will be ongoing by the study coordinator. These reports will be reviewed by the PI.

#### *7.7. Study conclusions*

Collected data from subjects will be reviewed to demonstrate that favorable changes are noted in biomarkers of body composition and age-related biomarkers with administration of the proprietary food products. Data will be evaluated for change from baseline over time within arms and for differences between the intervention arm and the control arm.

##### *7.7.1. Analysis supporting primary objectives*

Generalized mixed linear models will be used to compare arm 1 (FMD) to the arm 3 (control group) sitting fat mass expressed in terms of change from baseline to the end of the 3 FMD cycles (month 6, visit 3). The analysis will include the fixed categorical effect of treatment, a fixed term modelling changes between baseline and other time periods, as well as a random term accounting for repeated measurements on the same patients. The same analyses will be used to compare arm 2 to the arm 3, sitting fat mass expressed in terms of change from baseline to the end of the study (month 6).

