##### *7.7.2. Analysis supporting secondary objectives*

Generalized mixed linear models will be used as previously described to compare arm 1 and arm 2 vs arm 3, sitting the following parameters expressed in terms of change from baseline to the end of the study (month 6): inflammatory biomarkers (CRP, etc), IGF-1, blood pressure, serum lipids, glucose, CV biomarkers and, body weight, BMI, body composition, insulin resistance, aging biomarkers, sleep quality and duration, and number of participants who receive antihypertensive/hypoglycaemic medications.

We will also evaluate the effect of FMD and FMD+LD treatments on risk factors for CVD and metabolic syndrome, defined as three of five of the following conditions: abdominal obesity, elevated fasting glucose, elevated blood pressure, high serum triglycerides, and low HDL cholesterol.

We will select clinically relevant cutoffs and compared normal and at-risk subjects for each risk factor: total cholesterol >199 mg/dl and LDL cholesterol levels >130 mg/dl are associated with an increased risk for CVD, a fasting glucose >99 mg/dl indicates impaired fasting glucose/prediabetes, and triglyceride levels >100 mg/dl as well as CRP >1 mg/liter are associated with increased risk for CVD. For serum IGF-1, no clinically relevant risk level has been established, but a number of epidemiological studies have associated IGF-1 levels above 200 ng/ml with various cancers (Levine et al., 2014; Pollack et al., 2007). We will therefore compare the effect of FMD/FMD + LD cycles on subjects in the highest quartile of IGF-1 expression (>225 ng/ml) with that on subjects with IGF-1 levels ≤225 ng/ml. The effect of FMD and FMD+LD treatments on these risk factors will be assessed also stratifying our sample by baseline BMI, SBP and DBP, fasting glucose, cholesterol, CRP and IGF-

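### Section 7.4 sizes the trial on a time × intervention interaction, but 7.7.1 lists no interaction and pairs repeated-measures terms with one month-6 change; the response and the month-6 contrast should be named.

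*Protocol*

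**What the plan says.** Protocol 7.4 bases the sample size on detecting "a significant effect of FMD nutritional intervention on fat mass during the treatment period (6 months) with respect to the control group". It frames the hypothesis as an interaction between time and intervention, in a sentence that begins "The primary hypothesis of this trial can be formally stated as a test of whether there is a time". With Cohen's f = 0.10, a correlation of 0.5 between repeated measures and a significance level of 0.05, "a sample size of 107 participants per group, would give a power of at least 0.9". The numbers of groups and measurements are not given.

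Protocol 7.7.1 compares arm 1 with arm 3 on "sitting fat mass expressed in terms of change from baseline to the end of the 3 FMD cycles (month 6, visit 3"), and then arm 2 with arm 3 in the same way at month 6. On the model it says: "The analysis will include the fixed categorical effect of treatment, a fixed term modelling changes between baseline and other time periods". A third element completes the list: "as well as a random term accounting for repeated measurements on the same patients".

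The Protocol Summary (Efficacy assessments) and 2.2.1 also define the outcome as a change from baseline to the last visit. Section 7.7.2 reuses the 7.7.1 model for the secondary outcomes, each "expressed in terms of change from baseline to the end of the study (month 6"). Table 1 and 3.3.3–3.3.5 schedule bioimpedance at baseline (T0), visit 2 (T1) and visit 3 (T2).

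**The concern.** One month-6 change per patient leaves nothing for a time term or a repeated-measures random term to estimate. Those terms need several values per patient, which the response clause does not provide. An analyst must drop part of the paragraph, and which part is dropped decides what the treatment coefficient means.

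If the terms are kept and the visit data are modelled, a model with arm and time but no interaction gives one arm difference averaged over the visits. That is not the difference at month 6, and when baseline is among the visits it is not a test of the hypothesis in 7.4. The trial is open-label, so the choice should be settled before data are seen. Section 7.7 also promises more than an additive model can supply separately by arm: "Data will be evaluated for change from baseline over time within arms and for differences between the intervention arm and the control arm". That is a general statement, however, and does not bind the 7.7.1 model.

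**Working it through.** **Reproducing 107.** The inputs from 7.4 are f = 0.10, ρ = 0.5, α = 0.05. For an interaction with k groups, m measurements and N = k × n, use a noncentral F with λ = f²·N·m/(1−ρ) and df = (k−1)(m−1), (N−k)(m−1).

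| Design | λ at n = 107 | df | Power at 107 | Smallest n for 0.90 |
|---|---|---|---|---|
| 2 groups × 3 visits | 0.01·214·3/0.5 = 12.84 | 2, 424 | 0.902 | 107 (106 gives 0.899) |
| 3 groups × 2 visits | 0.01·321·2/0.5 = 12.84 | 2, 318 | 0.902 | 107 (106 gives 0.899) |
| 2 groups × 2 visits | 0.01·214·2/0.5 = 8.56 | 1, 212 | 0.830 | 133 |
| 3 groups × 3 visits | 0.01·321·3/0.5 = 19.26 | 4, 636 | 0.956 | 87 |

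So 107 is correct under two designs. The dropout step also reproduces: 107/0.7 = 152.9, rounded up to 153. Section 7.4 names FMD against control, and bioimpedance is scheduled three times, so 2 × 3 is the likelier design. Either way it is a 2-df test. The comparison of two arms on one month-6 change corresponds to 2 × 2.

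**Month-6 effect implied by f (2 × 3).** Let the arm difference at T0, T1, T2 be D times a profile. Interaction effects are half the centred profile with opposite signs in the two arms, so f² = D²·SS/12 and D = 0.1·√(12/SS), where SS is the centred sum of squares. The onset profiles are my assumptions:
- linear (0, ½, 1): SS = 0.500, D = 0.490 SD
- per FMD cycle (0, ⅔, 1): SS = 0.519, D = 0.481
- early (0, 1, 1): SS = 0.667, D = 0.424
- late (0, 0, 1): SS = 0.667, D = 0.424

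**What the treatment term estimates.** Take SD 1 at each visit, ρ = 0.5, complete data, 107 per arm and two-sided α 0.05 per comparison. The subject-level variances are:
- (a) month-6 change: 2(1−ρ) = 1
- (b) mean of the changes at T1 and T2: (1+ρ)/2 + 1 − 2ρ = 0.75
- (c) mean of measured values at T0, T1, T2: (1+2ρ)/3 = 0.667
- baseline-adjusted month-6 value: 1−ρ² = 0.75

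The share of the month-6 effect is the average of the profile over the visits used. Power is by noncentral t with ncp = share·D/√(2·variance/107). For linear onset under (c) this is 0.5·0.490/√(2·0.667/107) = 2.19, giving 0.59.

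| Onset | (a) month-6 change | (b) changes at T1 and T2 | (c) measured values T0–T2 | Baseline-adjusted T2 difference |
|---|---|---|---|---|
| Linear | 100%, 0.95 | 75%, 0.87 | 50%, 0.59 | 100%, 0.98 |
| Per cycle | 100%, 0.94 | 83%, 0.92 | 56%, 0.66 | 100%, 0.98 |
| Early | 100%, 0.87 | 100%, 0.95 | 67%, 0.71 | 100%, 0.95 |
| Late | 100%, 0.87 | 50%, 0.43 | 33%, 0.24 | 100%, 0.95 |

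**The case against.** The strongest reply is that a treatment effect on change from baseline already is a time × intervention contrast. On that view no interaction term is missing, and 7.4 and 7.7.1 agree in substance. The Summary, 2.2.1, 7.7.1 and 7.7.2 all state a change to month 6, so the low powers under (c) require an analyst to set aside the response given in the same paragraph. This stands: reading (a) is favoured, and under it the repeated-measures terms are merely idle.

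Reading (b) gives every listed term a role and, outside late onset, costs little power. That also stands, but (b) still does not name the month-6 contrast.

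The sizing design can largely be inferred from 7.4 and Table 1, so leaving it unstated is a gap in reporting and not an error in the number. The powers above use 107 per arm; 167 with 30% dropout leaves about 117, where (a) reaches 0.90–0.96.

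Finally, 7.1 calls the study exploratory, and covariance structure and covariates are commonly left to an SAP. But the protocol itself fixes the hypothesis, the response and the terms, and an SAP would have to depart from one of them.

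**Conclusion.** The inconsistency is real and should be fixed: the protocol does not determine one primary estimate. Depending on which words are followed, the treatment term carries all of the month-6 effect (a), 50–100% of it (b) or 33–67% of it (c). Power runs from 0.24 to 0.95 against a planned 0.90. These figures rest on f = 0.10 and ρ = 0.5 from 7.4, 107 per arm, a 2 × 3 sizing design and the four assumed onset patterns.

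A reader might infer that the primary analysis is biased, or that it will report about half the true effect. The documents do not support this: no bias arises under the favoured reading, and the dilution depends on the reading and on the onset. A reader might also infer that the sample size is wrong. It is not: 107 reproduces exactly. What is missing is the statement that it is a 2-df interaction test and not the pairwise month-6 comparison that 7.7.1 reports.

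**What to change.** In 7.7.1, state:
- response: percentage fat mass at T1 and T2;
- fixed effects: baseline percentage fat mass, arm, visit, arm × visit, and the stratification factors of 7.1 (sex, age group, BMI group);
- within-subject correlation modelled;
- primary test: the arm difference at T2, for arm 1 against arm 3 and for arm 2 against arm 3.

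The arm × visit term is there so that the T2 difference can be read off. It should not itself be the primary test, because with baseline as a covariate it is zero for an early, maintained effect.

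In 7.4, reword the primary hypothesis as this month-6 contrast and state the groups and measurements behind 107.

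The response, the named T2 contrast and the aligned 7.4 are the necessary parts. Baseline and strata adjustment is a free gain in precision, not the correction of an error: baseline alone cuts the variance of the month-6 contrast from 1 to 0.75 (25%) relative to the change score, giving power 0.95–0.98 for the four onset patterns.

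The cost is one model sentence in 7.7.1, two sentences in 7.4 and matching SAP text. No visit, measurement or participant is added.
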